### 7.2 **Safety/Tolerability**

Analyses will be performed for all patients having received at least one dose of study drug. The study will use the CTCAE version 5.0 for reporting of adverse events (<http://ctep.cancer.gov/reporting/ctc.html>).

## 8.0 **ADVERSE EVENTS**

### 8.1 **Adverse Event Report Requirements**

Adverse event (AE) monitoring and reporting is a routine part of every clinical trial and is done to ensure the safety of subjects enrolled in the studies as well as those who will enroll in future studies using similar agents. Data on adverse events will be collected from the time of informed consent through 30 days after the last dose of study treatment. Any serious adverse event that occurs more than 30 days after the last study treatment and is considered related to the study treatment must also be reported. Serious Adverse Events (SAEs) will continue to be followed until:

- Resolution or the symptoms or signs that constitute the serious adverse event return to baseline;
- There is satisfactory explanation other than the study treatment for the changes observed; or
- Death.

The investigator is responsible for the detection, documentation, grading and assignment of attribution of events meeting the criteria and definition of an AE or SAE. The definitions of AEs and SAEs are given below. It is the responsibility of the principal investigator to ensure that all staff involved in the trial is familiar with the content of this section.

Any medical condition or laboratory abnormality with an onset date before initial study treatment administration is considered to be pre-existing in nature. Any known pre-existing conditions that are ongoing at time of study entry should be considered medical history.

All events meeting the criteria and definition of an AE or SAE, as defined in Section 8.2, occurring from informed consent through 30 days following the last dose of the study treatment must be recorded as an adverse event in the patient's source documents and on the CRF regardless of frequency, severity (grade) or assessed relationship to the study treatment.

In addition to new events, any increase in the frequency or severity (i.e., toxicity grade) of a pre-existing condition that occurs after the patient begins study treatment is also considered an adverse event.

Adverse events after the 30 day follow up period

For Pharmacovigilance purposes and characterization, any SAE of MDS/AML or new primary malignancy occurring after the 30 day follow up period should be reported to the Coordinating Center who in turn will report to AstraZeneca Patient Safety regardless of investigator's assessment of causality or knowledge of the treatment arm. Investigators will be asked during the regular follow up for overall survival if the patient has developed MDS/AML or a new primary malignancy and prompted to report any such cases.

At any time after a patient has completed the study, if an Investigator learns of any SAE including sudden death of unknown cause, and he/she considers there is a reasonable possibility that the event is causally related to the investigational product, the investigator should notify the Coordinating Center who in turn will notify AstraZeneca, Patient Safety.

If patients who are gaining clinical benefit are allowed to continue study treatment post data cut off and/or post study completion, then all SAEs must continue to be collected and reported to Patient Safety within the usual timeframe.

Otherwise, after study treatment completion (i.e. after any scheduled post treatment follow-up period has ended) there is no obligation to actively report information on new AEs or SAEs occurring in former study patients. This includes new AEs/SAEs in patients still being followed up for survival but who have completed the post treatment follow up period (30 days).

## 8.2 Definitions

### 8.2.1 Adverse Event

An adverse event (AE) is any untoward medical occurrence in a patient receiving study treatment and which does not necessarily have a causal relationship with this treatment. An AE can be any unfavorable and unintended sign (including an abnormal laboratory finding), symptom, or disease temporally associated with the use of an experimental intervention, whether or not related to the intervention.

- This includes any occurrence that is new in onset or aggravated in severity or frequency from the baseline condition.
- Diagnostic and therapeutic non-invasive and invasive (i.e. surgical) procedures will not be reported as adverse events. However, the medical condition for which the procedure was performed must be reported if it meets the definition of an adverse event unless it is a pre-existing (prior to protocol treatment) condition.

---

- Symptoms of the original or targeted disease are not to be considered adverse events for this study. The following symptoms are indicative of underlying disease and will not be reported as adverse events (unless the event is considered serious):
  - Cancer-related pain
- Abnormal laboratory values or test results constitute adverse events if they induce clinical signs or symptoms or require therapy. They are to be captured under the signs, symptoms or diagnoses associated with them.

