### 3.1 Inclusion Criteria

- 3.1.1 Advanced unresectable or metastatic sarcoma
  - Cohort 1: LMS/LPS
  - Cohort 2: Other histologies (excluding Gastrointestinal Stromal Tumors)
- 3.1.2 Must have received at least 1 prior standard systemic therapy regimen. For cohort 1 patients, this must have included a prior anthracycline.
- 3.1.3 Measurable disease by RECIST 1.1 criteria
- 3.1.4 Age  $\geq$  16 years
- 3.1.5 ECOG  $\leq$  1
- 3.1.6 Adequate hematologic, renal and hepatic function within 14 days prior to administration of study treatment as defined below:

Hemoglobin	$\geq 10$ g/dL with no blood transfusion within 28 days
Absolute neutrophil count	$\geq 1.5 \times 10^9$ /L
Platelets	$\geq 100 \times 10^9$ /L

Total Bilirubin	$\leq 1.5 \times$ institutional upper limit of normal (ULN).  NOTE: patients with elevated bilirubin secondary to Gilbert's disease are eligible to participate ( $<2.0 \times$ ULN should be used)
Aspartate aminotransferase (AST) & alanine aminotransferase (ALT)	$\leq 2.5 \times$ institutional ULN unless liver metastases are present in which case AST and ALT must be $\leq 5 \times$ ULN
Serum creatinine	Estimated or calculated creatinine clearance (Cockcroft-Gault formula) $\geq 51$ mL/min using the Cockcroft-Gault equation or based on a 24-hour urine test:  Estimated creatinine clearance = $(140 - \text{age} [\text{years}]) \times \text{weight} (\text{kg}) \times F^a$ serum creatinine (mg/dL) $\times 72$ a where F=0.85 for females and F=1 for males.

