## 5.2 Toxicities and Dosing Delays/Dose Modifications

Any patient who receives treatment on this protocol will be evaluable for toxicity. Each patient will be assessed for the development of toxicity according to the Time and Events Table (Section 6.2). Toxicity will be assessed according to the NCI Common Terminology Criteria for Adverse Events (CTCAE), version 5.0. Dose adjustments should be made according to the system showing the greatest degree of toxicity. Any toxicity observed during the course of the study could be managed by interruption of the dose of study treatment or dose reductions. Repeat dose interruptions are allowed as required, for a maximum of 4 weeks on each occasion. If the interruption is any longer, the study team must be informed. Once dose is reduced, escalation is not permitted

Table 1. Dose Level Reductions of Trabectedin and Olaparib

Dose Levels	Trabectedin	Olaparib
1 (starting)	1.1 mg/m 	150 mg BID
-1	0.94 mg/m 	100 mg BID
-2	0.8 mg/m 	

Criteria for start of new cycle:

- Platelet  $\geq$  100,000/microliter
- Absolute neutrophil count  $\geq$  1000/microliter
- Hemoglobin  $\geq$  9g/dl
- Total bilirubin  $\leq$  1.5 upper limit of normal (ULN)
- Aspartate aminotransferase (AST) and alanine aminotransferase (ALT)  $\leq$  2.5 x ULN
- Alkaline phosphatase (ALP)  $\leq$  2.5 x ULN
- Creatine phosphokinase (CK)  $\leq$  2.5 x ULN
- All non-hematologic toxicities considered related to study treatment must be  $\leq$  grade 2
- Absence of any subjectively intolerable grade 2 adverse event not controlled by supportive therapy

If a patient does not meet criteria to initiate a new cycle of treatment within 28 days of initial medication hold, or requires more than two dose reductions of trabectedin or one dose reduction of olaparib, they should be removed from study treatment.

For hematologic toxicities which meet parameters for dose hold, medication should be held per guidance below. Medication should be resumed at the reduced dose designated below. If AE is recurrent/persistent despite dose reduction as specified below, drug should be discontinued.

Table 2. Criteria for Dose modification of Thrombocytopenia, Neutropenia and Leukopenia

Laboratory Result	Dose Adjustments

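### The protocol is inconsistent on whether an untreated, asymptomatic laboratory toxicity is an adverse event, and the planned safety tables count adverse events only

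*Combined protocol and SAP*

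**What the plan says.** Section 8.2.1 opens broadly: "An AE can be any unfavorable and unintended sign (including an abnormal laboratory finding), symptom, or disease". Its first bullet also takes in anything new or aggravated relative to baseline. The last bullet is the only test specific to laboratory results: "Abnormal laboratory values or test results constitute adverse events if they induce clinical signs or symptoms or require therapy". It goes on: "They are to be captured under the signs, symptoms or diagnoses associated with them".

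Section 8.1 requires CRF recording of "All events meeting the criteria and definition of an AE or SAE, as defined in Section 8.2", so the recording duty inherits whatever 8.2 means. It also states: "Any medical condition or laboratory abnormality with an onset date before initial study treatment administration is considered to be pre-existing in nature". It then makes an adverse event of "any increase in the frequency or severity (i.e., toxicity grade) of a pre-existing condition that occurs after the patient begins study treatment", with no condition about symptoms or therapy.

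Section 5.2 uses adverse-event language for toxicities defined by a value. On hematologic toxicities that trigger a hold it says "If AE is recurrent/persistent despite dose reduction as specified below, drug should be discontinued". It calls neutropenia and leukopenia adverse events, and the title of Table 4 describes its bilirubin, AST/ALT, ALP and CK thresholds as laboratory adverse events.

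The safety endpoint in 2.4 is the occurrence of adverse events graded by CTCAE v5.0. Secondary item (c) of 11.3 tabulates adverse events seen in at least 5% of participants, and grade 3-5 rates, within each cohort. Sections 2.4, 7.2 and 11.3 plan no table of laboratory results by CTCAE grade and no summary of dose modifications.

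**The concern.** Secondary objective 2.2.3 is to describe safety and tolerability, and in a single-arm study the adverse-event table is the planned output for it. Section 1.3 reports that the dose-limiting toxicities of the combination in phase 1b were thrombocytopenia and prolonged neutropenia. These are the event types most exposed to the ambiguity, since a low count can trigger a dose hold without causing symptoms or needing treatment.

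With two centers, identical events could be recorded differently. The grade 3-5 table could then understate hematologic toxicity and fail to match the dose-modification record. Source verification (section 14.0) and quarterly review (section 12.0) may show that the centers differ, but neither says which reading is right.

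**Working it through.** There is no planned figure to reproduce. The check sets the texts side by side and then works out what one unrecorded patient does to a tabulated rate.

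**Step 1. Classify the same events under each reading.**

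| Event on treatment | 8.2.1 opening and first bullet, 5.2 wording | Laboratory bullet read as *only if* |
|---|---|---|
| Grade 4 neutropenia, no fever or infection, untreated, olaparib interrupted (Table 2) | Points to AE | Not an AE, unless a dose hold counts as therapy |
| Grade 3 thrombocytopenia, no symptoms or transfusion, olaparib interrupted (Table 2) | Points to AE | Not an AE, on the same proviso |
| Febrile neutropenia, or a cytopenia needing transfusion | AE | AE |
| ALT normal at entry, asymptomatic rise above the Table 4 threshold | Points to AE | Not an AE, on the same proviso |
| ALT above normal at entry, asymptomatic rise in grade | Points to AE | AE through the 8.1 grade-increase rule |

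The documents do not say whether a hold or reduction amounts to requiring therapy; on a plain reading it does not. The capture instruction adds to the doubt, because an asymptomatic value may have no associated sign or symptom to be filed under.

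The last two rows can arise because section 3.1 admits AST/ALT up to 2.5 x ULN (5 x ULN with liver metastases) and CK up to 2.5 x ULN. That contrast is an inference: it appears only if the bullet governs new values while 8.1 governs worsening ones.

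**Step 2. Confirm that 5.2 acts on values alone.** In Table 2, grade 3 and grade 4 thrombocytopenia and grade 4 neutropenia interrupt olaparib without any symptom condition, and these are grade 3-4 by definition. All four rows of Table 4 act on multiples of ULN, which the documents do not map to CTCAE grades. In Table 3, a recurrent hemoglobin of at least 8 but below 9 g/dl also interrupts olaparib on the value. This shows where a dose change can occur with no adverse event under the narrow reading. It does not count missed events.

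**Step 3. Effect on one row of the planned table.** Section 11.3 tabulates by preferred term. If k patients with a given term are unrecorded among N treated, the rate for that term falls by k/N. N comes from 11.2, assuming every enrolled patient receives at least one dose (the safety population in 7.2). For k = 1:

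- Cohort 1, full: 1/26 = 3.8 points
- Cohort 2, full: 1/27 = 3.7 points
- Cohort 1, stopped at stage 1: 1/16 = 6.3 points
- Cohort 2, stopped at stage 1: 1/13 = 7.7 points

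The documents give no basis for k. For scale only, assuming k from 1 to 3, the range is 3.8 to 11.5 points (3/26) in cohort 1 and 3.7 to 11.1 points (3/27) in cohort 2.

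**Step 4. Check whether the data exist to repair the table.** Section 6.2 schedules CBC and chemistry on days 1 and 15 of every cycle and on day 8 of cycles 1 and 2, with CK on day 1. That gives five CBC and chemistry draws per patient after the first dose within cycles 1-2 (C1D8, C1D15, C2D1, C2D8, C2D15). Section 5.2 requires dose reductions and interruptions, with reasons, to be recorded.

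**The case against.** The strongest reply is that a broad definition followed by a specific bullet is ordinary drafting, and that nearly all the other text points to inclusion: the opening of 8.2.1, its first bullet, the 8.1 grade-increase rule, the language of 5.2, and 8.3.1, which uses CTCAE terms and grades for reporting. Under-recording requires a center to read *if* as *only if* and set the rest aside. This stands to the extent that a reader might infer that 8.2.1 excludes asymptomatic laboratory toxicities, and it does not do so. What remains is that the bullet is the only laboratory-specific test, and a data manager following it literally would not be plainly wrong.

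A second reply is that little is lost. Symptomatic or treated events are captured on either reading, laboratory values and dose changes are retained, CRFs are source-verified, and the objective is descriptive with no test attached. This also stands: the weakness lies in the planned table and not in the data.

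A third concerns the remedy. A rule that ignored baseline and recorded every abnormality leading to a delay would clash with 8.1. A patient with liver metastases may enter with AST/ALT at 4 x ULN, while the new-cycle criteria and Table 4 act at 2.5 x ULN. An unchanged entry value could then become an adverse event although 8.1 calls it pre-existing. The objection is correct, and the recording rule has to be tied to change from baseline.

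**Conclusion.** The inconsistency is real and worth correcting. On a literal reading of the laboratory bullet, uncomplicated grade 3-4 neutropenia and thrombocytopenia could be missing from the grade 3-5 table at one center and present at the other, and 11.3 contains nothing that would compensate.

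The known size is the per-patient step for a preferred term: 3.8 points in cohort 1 and 3.7 in cohort 2 at full enrollment, or 6.3 and 7.7 at a stage 1 stop, with every enrolled patient treated. The number of patients affected cannot be derived from the documents.

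A reader might infer that safety data will be lost, or that toxicity rates will be understated by a definite amount. Neither is supported: the values are kept, and the effect depends on how each center reads the bullet. The primary endpoint and the Simon decision rules do not depend on adverse-event recording and are untouched.

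**What to change.** 1. Reconcile 8.2.1 with 8.1 and 5.2 in one recording rule for both centers. A laboratory abnormality that is new or has worsened in CTCAE grade from baseline is recorded under its own CTCAE term and grade if it either reaches a grade chosen by the study team (for example grade 3 or higher) or leads to a hold, delay, reduction or discontinuation of either drug. An unchanged pre-existing value, such as AST/ALT up to 5 x ULN at entry with liver metastases, stays pre-existing under 8.1. The threshold is the team's choice; what is needed is a single stated rule.

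2. In secondary item (c) of 11.3, add by cohort a table of baseline against worst post-baseline CTCAE grade for hematology, liver tests and CK, and a summary of recorded dose holds, reductions and discontinuations with reasons. The laboratory table is informative whichever way a center has recorded adverse events.

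The cost is wording in 8.1 and 8.2.1 and two added summaries. No new samples are needed and no dosing rule changes. The downside is some extra adverse-event entries and analysis work, and reported toxicity rates may be higher.

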#### 8.2.2 Adverse Event of Special Interest

Adverse events of special interest (AESI) are events of scientific and medical interest resulting from a previously identified signal (even if non-serious) or are specific to the further understanding of a drug's safety profile. AESIs require close monitoring and rapid communication by the Coordinating Center to AstraZeneca and Janssen.

There are currently no Adverse Events of Special Interest for Yondelis (trabectedin) that will be reported to the Company.

Additional safety events of interest for trabectedin that require expedited reporting and/or safety evaluation include, but are not limited to:

- Drug exposure during pregnancy (maternal and paternal)
- Overdose of a Janssen medicinal product
- Exposure to a Janssen medicinal product from breastfeeding
- Suspected abuse/misuse of a Janssen medicinal product
- Inadvertent or accidental exposure to a Janssen medicinal product
- Any failure of expected pharmacological action (i.e., lack of effect) of a Janssen medicinal product
- Medication error involving a Janssen medicinal product (with or without patient exposure to the Janssen medicinal product, e.g., name confusion)
- Suspected transmission of any infectious agent via administration of a medicinal product
- Unexpected therapeutic or clinical benefit from use of a Janssen medicinal product

#### Olaparib

Adverse Events of Special Interest for olaparib are the Important Potential Risks of MDS/AML, new primary malignancy (other than MDS/AML) and pneumonitis.

A questionnaire will be sent to any investigator reporting an AESI, as an aid to provide further detailed information on the event. During the study there may be other events identified as AESIs that require the use of a questionnaire to help characterize the event and gain a better understanding regarding the relationship between the event and study treatment.

AESIs should not be reported as SAEs unless they meet the SAE reporting criteria per section 8.2.4.

Any AESI that is to be reported to Janssen and AstraZeneca by the Coordinating Center should be recorded on a Serious Adverse Event Report Form and be reported to Janssen and AstraZeneca **within 24 hours of knowledge of the event.**

### 8.2.3 **Product Quality Complaint (PQC) (for trabectedin only)**

A product quality complaint is defined as any suspicion of a product defect related to a potential quality issue during manufacturing, packaging, release testing, stability monitoring, dose preparation, storage or distribution of the product, or delivery system. Not all PQCs involve a subject. Lot and batch numbers are of high significance and need to be collected whenever available.

Examples of PQC include but not limited to:

- Functional Problem: e.g., altered delivery rate in a controlled release product
- Physical Defect: e.g. abnormal odor, broken or crushed tablets/capsules
- Potential Dosing Device Malfunction: e.g., autoinjector button not working, needle detaching from syringe
- Suspected Contamination
- Suspected Counterfeit

### 8.2.4 **Serious Adverse Event**

An adverse event is considered “serious” if, in the view of the Sponsor-Investigator, it results in any of the following outcomes:

- Death

If death results from (progression of) the disease, the disease should be reported as event (SAE) itself.

The cause of death of a subject in a study within 30-days of the last dose of study treatment, whether or not the event is expected or associated with the study drug, is considered a serious adverse event.

**NOTE: DEATHS FOR ANY REASON SHOULD BE REPORTED WITHIN THE PROTOCOL SPECIFIED SAE REPORTING PERIOD AS OUTLINED IN SECTION 8.4**

- A life-threatening adverse event

An adverse event is considered ‘life-threatening’ if, in the view of the investigator, its occurrence places the patient or subject at immediate risk of death. It does not include an adverse event that, had it occurred in a more severe form, might have caused death.

- Inpatient hospitalization or prolongation of existing hospitalization

- A persistent or significant incapacity or substantial disruption of the ability to conduct normal life functions

- A congenital anomaly/birth defect

- Important medical event

Any event that may not result in death, be life-threatening, or require hospitalization may be considered serious when, based upon appropriate medical judgment, they may jeopardize the patient and may require medical or surgical intervention to prevent one of the outcomes listed in this definition of “Serious Adverse Event”. Examples of such medical events include allergic

bronchospasm requiring intensive treatment in an emergency room or at home; convulsions that do not result in inpatient hospitalization or the development of drug dependency or drug abuse; or suspected transmission of any infectious agent via a medicinal product.

Previously planned (prior to signing the informed consent form) surgeries should not be reported as SAEs unless the underlying medical condition has worsened during the course of the study. Preplanned hospitalizations or procedures for preexisting conditions that are already recorded in the patient's medical history at the time of study enrollment should not be considered SAEs. Hospitalization or prolongation of hospitalization without a precipitating clinical AE (for example, for the administration of study therapy or other protocol-required procedure) should not be considered SAEs. However, if the preexisting condition worsened during the course of the study, it should be reported as an SAE.

